Participants:

[figure not shown]
Inclusion Criteria: We will enroll 60 veterans with PTSD. To be eligible for the study, participants must meet current DSM-V diagnostic criteria for PTSD (American Psychiatric Association, 2013). PTSD will be established by interview using the Clinician Administered Posttraumatic Stress Disorder Scale for the DSM-V (CAPS-5; Weathers et al., 2013a). Participants must also indicate current difficulties with anger and aggression as indicated by a score of 20 or higher on the trait anger scale of the State Trait Anger Expression Inventory-2 (STAXI-2, Spielberger, 1999), indicating moderate to severe anger problems. Veterans from all eras will be eligible to participate.

Exclusion Criteria: Participants with a current diagnosis of bipolar disorder, psychotic disorder, or current substance use disorder with severe symptoms. Participants also must not have a seizure disorder and must not be taking any medications that would affect cognition or behavior on the aggression task, including pain medication, benzodiazepines, or antipsychotics. Participants also must not have a positive drug (e.g., amphetamine, opiates, and cocaine) or alcohol urine screen at the post-treatment session (see below), as these substances could affect performance on the study tasks implemented at that session. Finally, participants must not currently be receiving concurrent individual therapy or group therapy focused on anger and aggression and must not currently be participating in the modified TREC group offered at the West Haven VA (WHVA).

Research Design and Methods

For an overview of the time line for study procedures, see Figure 2.

Figure 2. Timeline of Study Procedures

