Trauma Scripting Procedure. After completing the diagnostic interviews (CAPS-5/SCID-5-RV), eligible participants will participate in a trauma-script development procedure as part of a well-validated, script-driven trauma imagery task (Pitman et al., 1987). For this procedure, participants will be asked to identify their most traumatic experience. If they identify more than one event, they will be asked to choose the one that they consider the most distressing. They will first be asked to describe the experience in writing using a script preparation form and then will be asked to indicate which of several different subjective visceral and muscular reactions (e.g., heart beating slower/faster, feeling sweaty, stomach in knots, feeling warm, hands trembling, tension in arms, nausea) may have accompanied the experience. Participants’ written responses will then be reviewed and they will be asked to clarify or expand on the details if necessary. After the session, a script lasting approximately 60 seconds in duration will be composed that portrays the traumatic experience in the second person, present tense, and incorporates the different visceral or muscular reactions. The script will then be audio recorded for playback

during the experimental portion of the post-treatment session. A research assistant (who will be named later upon being hired) will read the narrative scripts to be audio-recorded.

During this baseline session, participants will also complete a battery of self-report questionnaires (see below for full details) to assess baseline levels of anger and aggression.

Randomization Procedures. After participants have completed the Baseline Screening and Evaluation Session they will be randomized to either the TREC group or the MBSR group. To decrease the amount of time participants have to wait before starting group treatment, randomization will be implemented at the group level. That is, after 6 participants are recruited, they will be randomly assigned using urn randomization procedures, to either the TREC group or the MBSR group.

Post-treatment Session: After all participants have completed their assigned interventions (TREC or MBSR) they will be scheduled for the post-treatment session to be held in the biological studies laboratory at the WHVA. At this session, all participants will complete a battery of self-report questionnaires to assess post-treatment levels of anger and aggression (see below).

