| Diagnostic Assessments | | | | | |
| Clinician Administered PTSD Scale for DSM-V: Past-Month Version (CAPS-5) | X | | | | |
| Structured Clinical Interview for DSM-5 Disorders-Research Version (SCID-5-RV) | X | | | | |
| Life Events Checklist-5 (LEC) | X | | | | |
| Primary Outcome Measures: Self-Report | | | | | |
| State Trait Anger Expression Inventory-2 (STAXI-2) | X | X | X | X | X |
| Buss-Perry Aggression Questionnaire (BPAQ) | X | X | X | X | X |
| Primary Outcome Measure: Experimental | | | | | |
| Taylor Reaction Time Task (TRT) | | | | X | |
| Secondary Outcome Measures | | | | | |
| Physiological Reactivity: Heart Rate, Skin Conductance | | | | X | |
| Emotion Regulation: State Difficulties in Emotion Regulation Scale (DERS-S) | | | | X | |
| Exploratory Outcome Measures | | | | | |
| Five Facet Mindfulness Questionnaire (FFMQ) | X | X | X | X | X |
| PTSD Checklist for the DSM-V (PCL-5) | X | X | X | X | X |
| Quantity-Frequency Variability Index (QFI) | X | X | X | X | X |
| Alcohol Dependency Scale (ADS) | X | X | X | X | X |

Baseline Session:

(a) PTSD, other psychiatric disorders, anger and aggression:

The DSM-V criteria for PTSD will be established using the Clinician Administered PTSD Scale: Past-Month Version (CAPS-5, Weathers et al., 2013a). The CAPS-5 will be used to confirm DSM-V PTSD diagnosis and to provide a continuous measure of PTSD severity (CAPS-5 total score). To facilitate the administration of the CAPS, participants will also complete the Life Events Checklist-5 (LEC; Weathers et al., 2013b), which is a self-report questionnaire used to assess the extent to which individuals experienced any of 17 different stressful or difficult life events (e.g., combat exposure, natural disaster, fire or explosion).

Participants will be assessed for psychiatric disorders at the baseline session using the Structured Clinical Interview for DSM-5 Disorders – Research Version (SCID-5-RV, First et al.,

2014). The information from the SCID will be used to exclude participants with severe psychiatric disorders (e.g., schizophrenia or bipolar disorder).

(b) Battery of Self-Report Questionnaires: Participants will also complete a battery of self-report questionnaires including assessments measuring anger and aggression, in addition to trait mindfulness, PTSD, and alcohol use:

- State Trait Anger Expression Inventory-2 (STAXI-2, Spielberger, 1999)
- Buss-Perry Aggression Questionnaire (BPAG; Buss and Perry, 1992)

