
Data Analyses

Data will first be subjected to data screening procedures. This will include examining the data through visual inspection to ensure there are no missing data or outliers and performing appropriate descriptive analyses to ensure that there are no violations to normality, homoscedasticity, multicollinearity, etc. To the extent that there are violations to assumptions of normality, transformations will be considered and utilized if necessary. Appropriate procedures also will be implemented to deal with any other potential violations of statistical assumptions using procedures outlined by Tabachnick & Fidell (2000).

Although random assignment will be utilized, follow-up statistical analyses will be conducted to ensure that there are no differences between the TREC and MBSR groups on demographic variables (e.g., age, ethnicity, education) in addition to differences between the two

groups on other variables that may include (but are not limited to) other psychiatric symptomatology and trait mindfulness. To the extent that there are differences on these variables, they will be included as co-variables in subsequent analyses. For all analyses, the extent to which participants are taking any medications, (categorized as ‘yes/no’) will be included as a statistical control.

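### Covariates are chosen by comparing the randomised arms on an open list and adjusting for whatever differs, so the adjusted model is set by chance imbalance and not fixed in advance; the rule also omits the word baseline.

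*Combined protocol and SAP*

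**What the plan says.** **The rule (Data Analyses).** After noting that assignment is random, the plan says that "follow-up statistical analyses will be conducted to ensure that there are no differences between the TREC and MBSR groups on demographic variables", and also between the "groups on other variables that may include (but are not limited to) other psychiatric symptomatology and trait mindfulness". It then says: "To the extent that there are differences on these variables, they will be included as co-variables in subsequent analyses". It gives no test, threshold, closed list or time point.

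**The one covariate fixed in advance (same section).** "For all analyses, the extent to which participants are taking any medications", coded yes/no, is a statistical control. Its time point is not given.

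**The primary model (Primary Aim 1, Hypothesis 1.1).** The fixed effects are treatment, time and their interaction. Subject is nested in therapy group, and both are random. No covariate list is given. The TRT, physiological and DERS-S analyses are to follow the same strategy.

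**Timing of measures (Table 1).** Trait mindfulness is scheduled at all five visits: "Five Facet Mindfulness Questionnaire (FFMQ) | X | X | X | X | X". PCL-5, STAXI-2 and BPAQ have the same schedule. The TRT, heart rate, skin conductance and DERS-S are measured at the post-treatment session only.

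**Allocation (Participants; Randomization Procedures).** "We will enroll 60 veterans with PTSD"; "randomization will be implemented at the group level"; "after 6 participants are recruited, they will be randomly assigned using urn randomization procedures".

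**The concern.** A comparison of randomised arms on a pre-randomisation variable tests a hypothesis known to be true, so any difference found is chance. What makes a covariate worth including is its relation to the outcome, and the rule does not look at that. A strong predictor of aggression that happens to be balanced is left out, and an irrelevant variable that happens to be imbalanced goes in.

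The open list and missing threshold add a second problem. The analyst decides, with the arms in view, which variables to examine and how large a difference counts.

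Third, the rule does not limit itself to baseline values, although two natural candidates (FFMQ and PCL-5) are measured again during and after treatment. Mindfulness is what MBSR teaches, so adjusting for a later FFMQ score would adjust for part of the treatment's own effect.

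**Working it through.** The plan states no figure on this point, so there is none to reproduce.

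**Inputs from the documents.** N = 60 in groups of 6, so 60/6 = 10 groups if all are full. Five candidates are named: age, ethnicity, education, psychiatric symptomatology and trait mindfulness. 

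**Assumptions (not in the documents).** Screening at 5% (10% as the upper end), independent candidates, equal allocation (30 per arm, 5 groups per arm), and ICC of a baseline variable from 0 to 0.10.

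**Step 1. Chance that the covariate set changes by luck.** P(at least one flagged) = 1 − (1 − α)^k.

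- k = 5, α = 0.05: 1 − 0.95^5 = 0.226.
- k = 5, α = 0.10: 1 − 0.90^5 = 0.410.
- The list is open. For k = 10 and α = 0.05 the figure is 1 − 0.95^10 = 0.401.

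Five yes/no decisions allow 2^5 = 32 covariate sets.

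**Step 2. If the checks ignore group randomisation.** Simulated individual-level t-tests (10 groups of 6, five per arm, 20,000 runs per ICC):

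| ICC | Rejection per variable | At least one of five |
|---|---|---|
| 0 | 5.1% | 23% |
| 0.02 | 5.9% | 26% |
| 0.05 | 7.9% | 34% |
| 0.10 | 11.2% | 45% |

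For example, at ICC 0.05: 1 − (1 − 0.0785)^5 = 0.335.

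**Step 3. Effect on the STAXI-2 and BPAQ contrast.** A baseline covariate x entered as a main effect adds the same βx to every visit of a participant. It cancels from that participant's change, (post + βx) − (baseline + βx), so with complete data the treatment-by-time contrast does not move. A simulated random-intercept model (60 participants, five visits, covariate imbalanced by 0.5 SD) agrees: the interaction estimate is the same with and without the covariate to rounding error. With dropout rising to 30% by the last visit, the mean shift was 0.01 on an outcome SD of about 1.1.

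**Step 4. Effect on a single-visit outcome.** Simulated ANCOVA: 30 per arm, individually randomised, five independent baseline covariates each correlated r with the outcome, no true effect, 10,000 runs.

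| r | Quantity | Unadjusted | Test-then-adjust | Fixed set |
|---|---|---|---|---|
| 0.2 | Empirical SE (SD units) | 0.257 | 0.253 | 0.240 |
| 0.2 | Type I error | 0.051 | 0.046 | 0.050 |
| 0.3 | Empirical SE (SD units) | 0.258 | 0.244 | 0.199 |
| 0.3 | Type I error | 0.049 | 0.037 | 0.047 |

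The variance under test-then-adjust relative to the fixed set is (0.253/0.240)² = 1.11 at r = 0.2 and (0.244/0.199)² = 1.50 at r = 0.3. Five independent covariates at r = 0.3 explain 5 × 0.09 = 45% of the outcome variance, and at r = 0.2 they explain 5 × 0.04 = 20%. The larger gain therefore needs good predictors.

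**Step 5. Room for choice.** At r = 0.3 with all 32 covariate sets fitted to one single-visit outcome, the treatment estimate ranged over a median of 0.30 SD. At least one set gave p < 0.05 in 17% of trials with no true effect. This is a ceiling for entirely free choice, not a prediction of what the sponsor would do.

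**Step 6. If a post-treatment FFMQ score were used.** Adjusted effect = total effect − (within-arm slope × effect on FFMQ). The total effect is assumed to be −0.50 SD.

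| MBSR effect on FFMQ | Chance it is flagged (5%, 30 per arm) | Adjusted effect, slope −0.3 | Adjusted effect, slope −0.5 |
|---|---|---|---|
| 0.3 SD | 21% | −0.41 | −0.35 |
| 0.5 SD | 49% | −0.35 | −0.25 |
| 0.8 SD | 87% | −0.26 | −0.10 |

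For example, −0.50 − (−0.5 × 0.5) = −0.25.

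**The case against.** The strongest reply has five parts.

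- **The main self-report result hardly depends on the rule.** This stands for covariates entered as baseline main effects (Step 3). It would not hold if covariates also interacted with time, and the plan does not say that they will.
- **False positives are not inflated.** This also stands for mechanical use on baseline values: the simulated type I error was 0.037. A reader might infer that the rule inflates type I error. The calculations do not show that, and the 17% in Step 5 requires free choice among models.
- **Baseline was meant.** Probably so. The sentence opens by conceding random assignment and reads as a randomisation check, and trait mindfulness is named in the baseline battery. A reader might infer that the plan calls for adjustment on post-randomisation mindfulness. It does not: the wording leaves this open, and nothing states it. The figures in Step 6 also assume that mindfulness lowers anger and that no other factor drives both.
- **The chance of a flag rests on assumptions.** True. A reader might infer that a third to a half of trials would be affected, but that needs about eight independent candidates and, for the upper end, clustering in variables measured before any group session. The five named candidates give 23%. The plan names no test, so it does not say that clustering would be ignored. These percentages count how often the covariate set changes, not how far the estimate moves.
- **Medication is prespecified.** Correct, so not every covariate is chosen by the rule. Its absence from Table 1 is no gap either, because that table is described as listing the primary assessments. Only its time point is missing.

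The pilot purpose also limits the harm. Effect sizes for the later trial come from two-sample t-tests (Sample Size and Power Considerations), which this rule does not touch.

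**Conclusion.** The concern holds as a fault in method with moderate consequences. The rule selects on chance imbalance instead of prognostic value, from a list that nothing else in the document closes. With the five named candidates, independent and tested at 5%, the covariate set changes by chance in about 23% of trials, and in about 34% if clustering is ignored at an assumed ICC of 0.05.

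The practical cost falls on the comparisons with no pre-randomisation measurement of the outcome: TRT, heart rate, skin conductance and DERS-S. There, a fixed prognostic set would give a smaller SE (0.199 against 0.244 SD at r = 0.3; 0.240 against 0.253 at r = 0.2) and remove the choice among models. These SEs come from an individually randomised, single-visit model, so they show direction and rough size and are not forecasts for the planned mixed model.

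For STAXI-2 and BPAQ the effect is small. The missing baseline restriction is an omission to close, not evidence of a planned bias. The point merits a correction to the plan, but does not by itself undermine the trial.

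**What to change.** Change the Data Analyses section as follows.

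1. Delete the test-then-adjust rule.
2. Prespecify a short covariate list. For the TRT, heart rate, skin conductance and DERS-S analyses, include baseline STAXI-2 trait anger and baseline BPAQ.
3. For STAXI-2 and BPAQ, state whether the baseline score stays in the response vector as a level of time or is a covariate. It should not be both. The current model text leaves this open.
4. Keep the medication yes/no covariate and state that it is recorded at baseline.
5. State that only values measured before randomisation may be covariates.
6. Report baseline characteristics by arm descriptively, without tests, and label any further adjustment as a sensitivity analysis.

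The cost is wording: sample size and visits are unchanged. The downside is that a chance imbalance in an unlisted variable is handled only in the sensitivity analysis.

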Primary Aim 1 Hypothesis 1.1: Participants assigned to MBSR will report decreased levels of self-reported anger and aggression at post-treatment and at the 3-month follow up compared to those assigned to the TREC group. Scores on the State Trait Anger Expression Inventory-2 and the Buss-Perry Aggression Questionnaire will be used as the primary outcome variables for self-report anger and aggression. Intent-to-treat analyses will be conducted for these outcomes, which will be examined separately. Bonferroni adjustments will be implemented to control for Type 1 error. These data will be analyzed using mixed effects models with treatment, time, and treatment x time interaction as fixed effects. Subject will be the clustering factor and it will be nested within therapy group which will also be considered random. Different variance-covariance structures will be considered and the best one selected based on Schwartz’ Bayesian Information Criterion (BIC). Mixed effects models are the preferred method for analyses of such data as they use all available data on an individual, give unbiased results under general missing data assumptions and provide flexibility in modeling the correlation structure within subject. Significant interactions will be examined further using post-hoc tests.

Primary Aim 1, Hypothesis 1.2: Participants assigned to MBSR will exhibit lower levels of anger and aggression on the TRT compared to those assigned to the TREC group. Mixed effects models will be used to compare the TREC group to the MBSR group on responses on the TRT: (1) mean shock level across the TRT, and (2) total number of “20” shocks chosen on the TRT following the same strategy as for primary aim 1 hypothesis 1.1.

Secondary Aim 1, Hypothesis 1.1: Those assigned to MBSR will exhibit significant decreases in HR and SCL and increases in emotion regulation compared to those assigned to the TREC group. Mixed effects models will be used to compare the TREC group to the MBSR group on physiological variables (HR, SCL) and emotion regulation (DERS-S) following the same strategy as for primary aim 1, hypothesis 1.1.

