Secondary Aim 1, Hypothesis 1.2: Within the MBSR group, decreases in physiological reactivity and increases in emotion regulation will be associated with decreases in aggression on the TRT. Pearson product moment correlations will be calculated to examine the association between changes in HR, SC, and emotion regulation and the TRT responses (i.e., mean shock level across the TRT and total number of “20” shocks chosen on the TRT).

Sample Size and Power Considerations

Although the proposed sample size may not be sufficient in establishing statistical significance but rather a pattern of results that suggest promising effects across anger outcomes, it is important to emphasize that the fundamental purpose of the pilot trial is to provide information for the planning of a future large scale clinical trial examining the efficacy of MBSR in decreasing anger and aggression in veterans with PTSD and examining additional mechanisms of action (i.e., behavioral, cognitive, social, biological) that lead to behavior change. To that end, the pilot RCT data will be used in power calculations to calculate the sample size for a later full-scale RCT examining MBSR for anger and aggression for veterans with PTSD.

Effect sizes for determining the sample size for the larger RCT will be calculated based on differences between the baseline and post-treatment scores on the self-report measures of

anger and aggression (STAXI-2, BPAQ), as well as the difference scores between the physiological measures (i.e., HR and SC) and emotion regulation obtained during the experimental portion of the post-treatment session. Comparisons will be made using a two-sample t-test. Due to the possibility that estimation of effect sizes based on pilot studies may be inaccurate (Kraemer et al., 2006), we will implement procedures recommended for improved characterization of effect sizes derived from pilot studies (Thabane et al., 2010). These include close consultation with clinicians who have used the treatment (i.e., [name]), and accounting for the effect size uncertainty by constructing confidence intervals around the observed effect size.

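### Medication is to be controlled in all analyses, but the within-MBSR Pearson correlations (Secondary Hypothesis 1.2) are specified without it

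*Combined protocol and SAP*

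**What the plan says.** Three places in the combined protocol and SAP bear on this.

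- **Data Analyses, opening paragraphs.** The rule is general: "For all analyses, the extent to which participants are taking any medications", reduced to yes or no, "will be included as a statistical control". Baseline variables on which the arms differ get similar treatment: "they will be included as co-variables in subsequent analyses". No method is named for analyses that have no place for a covariate.
- **Data Analyses, Secondary Aim 1, Hypothesis 1.2.** The hypothesis is confined to one arm: "Within the MBSR group, decreases in physiological reactivity and increases in emotion regulation will be associated with decreases in aggression on the TRT". The method is: "Pearson product moment correlations will be calculated to examine the association between changes in HR, SC, and emotion regulation and the TRT responses". The TRT responses are mean shock level and the number of 20 shocks. No partial correlation or regression is mentioned.
- **Sample Size and Power Considerations.** For the effect sizes that will inform the later trial: "Comparisons will be made using a two-sample t-test".

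The between-arm hypotheses use a different tool. Primary Hypothesis 1.1 specifies "mixed effects models with treatment, time, and treatment x time interaction as fixed effects", and Primary Hypothesis 1.2 and Secondary Hypothesis 1.1 follow the same strategy. Such models can carry the medication term.

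**The concern.** An analyst who runs the named Pearson correlation has not applied the plan's own control. An analyst who applies the control is running something the plan does not name. The choice would then be made after the data are in hand.

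This matters most for Secondary Hypothesis 1.2, the only specified hypothesis tested wholly within one arm. Randomisation balances medication between MBSR and TREC on average. It does nothing to balance medication across levels of physiological reactivity or emotion regulation within MBSR. If medicated and unmedicated veterans differ on both reactivity and shock choice, a correlation can appear with no direct link between the two. At least six correlations are involved: heart rate, skin conductance and emotion regulation, each against two TRT responses.

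The protocol gives some reason to take medication seriously. Exclusion Criteria bar drugs that could alter task behaviour, and Background notes that aggression paradigms are used to test pharmacotherapies. The yes/no term itself implies that some enrolled participants will be medicated.

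**Working it through.** **No stated figure to reproduce.** The plan gives no power, effect size, SD or numeric alpha, and no data on medication associations. The point is first a comparison of texts. The arithmetic shows how much it could matter under stated assumptions.

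**Comparison of texts.** The rule covers all analyses. The mixed models have room for the term. A zero-order Pearson correlation and a two-sample t-test, as named, do not.

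**Inputs**

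- Total sample 60 (Inclusion Criteria), randomised in batches of 6 (Randomization Procedures): 60/6 = 10 groups. The allocation ratio is not stated. Assumed: 5 groups per arm, so 5 × 6 = 30 in MBSR, with a range of 24 to 36.
- Assumed: two-sided 5% per correlation, half of the MBSR arm medicated, no true link between reactivity (X) and TRT response (Y), and medication shifting both by s residual SDs in the same direction.

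**Spurious correlation.** With half medicated, the medication indicator has variance 0.25. The covariance of X and Y is 0.25s² and each has variance 1 + 0.25s², so r = 0.25s²/(1 + 0.25s²). The rejection probability by Fisher z is Φ(m − 1.96) + Φ(−m − 1.96), with m = atanh(r) × √(30 − 3).

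| Shift s | r | m | False positives, Fisher z | Simulated (60,000 samples) |
|---|---|---|---|---|
| 0.5 | 0.0625/1.0625 = 0.059 | 0.31 | 6.1% | 6.1% |
| 0.8 | 0.16/1.16 = 0.138 | 0.72 | 11% | 10.9% |
| 1.0 | 0.25/1.25 = 0.200 | 1.05 | 18% | 18.2% |

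A partial correlation on the same indicator stays at about 5% in every row.

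**Same check on another scale.** If medication correlates a with each variable and there is no other link, r = a². At a = 0.3, r = 0.09 and simulated false positives are about 7.5%. At a = 0.5, r = 0.25 and they are about 27%. Results are nearly the same with 30%, 50% or 70% medicated.

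**What the yes/no term leaves behind.** The 5% above holds because the indicator was made the exact confounder. Suppose instead that only half of the medicated take a drug that matters, with s = 1.0.

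- Unadjusted, 50% medicated: 25% take an active drug, so r = (0.25 × 0.75)/(1 + 0.25 × 0.75) = 0.1875/1.1875 = 0.16, and false positives are about 13%.
- Adjusted for yes/no: the average within-stratum covariance is 0.5 × 0.25 = 0.125, so partial r = 0.125/1.125 = 0.11, and false positives are about 9%.
- With 70% medicated: r = 0.2275/1.2275 = 0.19 (about 16%) unadjusted, and 0.175/1.175 = 0.15 (about 12%) adjusted.

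**Price of adjustment.** Critical |r| = t/√(df + t²), with df = n − 2 for Pearson and n − 3 for a partial correlation with one covariate.

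| n in MBSR | Critical \|r\|, Pearson | Critical \|r\|, partial |
|---|---|---|
| 24 | 0.404 | 0.413 |
| 30 | 0.361 | 0.367 |
| 36 | 0.329 | 0.334 |

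At n = 30, power for a true r of 0.5 goes from 0.814 to 0.800, and for 0.3 from 0.363 to 0.351.

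**The case against.** **The texts can be reconciled.** A partial correlation is the Pearson correlation of two variables after a control has been removed. A general rule followed by a named statistic can be read as Pearson correlations controlling for medication. This stands in part: a reader might infer that the two passages cannot both be followed, and that is too strong. But the plan does not say that a partial correlation is meant, and the literal method omits the control.

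**Eligibility already removes the main drugs.** Exclusion Criteria rule out medications that could affect cognition or task behaviour, including pain medication, benzodiazepines and antipsychotics, and the telephone screen under Procedure asks about those three classes. This stands. A reader might infer that the correlations are in fact confounded. The documents do not show it; they support only that residual confounding by permitted medications is possible.

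**The visible harm needs large shifts.** Also correct. At 0.5 SD the excess is about one percentage point. Rates of 11% to 18% need permitted medications to shift both variables by 0.8 to 1.0 SD in the same direction, which nothing in the documents establishes.

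**The t-test is a separate matter.** A reader might extend the confounding argument to the planning effect sizes. That does not follow: the comparison is between randomised arms, and an unadjusted effect size is a legitimate planning choice. Chance imbalance with about ten randomised groups is possible, but it is not the within-arm problem.

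**It is a secondary analysis in a pilot.** The plan concedes that statistical significance may be out of reach, and the hypothesis speaks only of association. That lowers the severity. It does not remove the point, because the stated purpose includes planning further work on mechanisms.

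**Conclusion.** The inconsistency is real and minor. The plan promises medication control in every analysis, and the method named for Secondary Hypothesis 1.2 does not include it. That hypothesis is an association within one arm, so it is open to residual confounding by permitted medications.

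The size is unknown and ranges from negligible (about 6% false positives at a 0.5 SD shift in both variables) to material (about 18% at 1.0 SD). These figures assume 30 in MBSR, half medicated, no true link, same-direction shifts and a 5% two-sided test.

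For the planning t-test the issue is consistency only: the pilot's mixed-model estimates would be adjusted for medication and the effect size carried forward would not. The primary mixed models and Secondary Hypothesis 1.1 are unaffected.

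**What to change.** 1. Under Secondary Aim 1, Hypothesis 1.2, name partial correlations, or a regression of each TRT response on the mechanism score, with the yes/no medication term from the opening of Data Analyses. Say whether covariates added for baseline imbalance also enter.
2. Under Sample Size and Power Considerations, either take the planning effect sizes from a model with the same medication term, or state that the rule does not apply to this t-test.
3. Note in the interpretation of Hypothesis 1.2 that an any-medication indicator removes only part of a medication effect.

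Limiting the general rule to the mixed models would also make the text consistent, but it would leave Hypothesis 1.2 without the control, so the first change is preferable there.

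The cost is a change of SAP wording and, for the medication term, one degree of freedom per correlation, as tabulated above.
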